12.3.1 DF/HCC Expedited Reporting Guidelines

Investigative sites within DF/HCC will report AEs directly to the DFCI Office for Human Research Studies (OHRS) per the DFCI IRB reporting policy.

Other investigative sites will report AEs to their respective IRB according to the local IRB’s policies and procedures in reporting adverse events. A copy of the submitted institutional AE form should be forwarded to the Overall PI within the timeframes detailed in the table below.

The Overall PI will submit AE reports from outside institutions to the DFCI OHRS according to DFCI IRB policies and procedures in reporting adverse events.

Attribution	DF/HCC Reportable AEs				
	Gr. 2 & 3 AE Expected	Gr. 2 & 3 AE Unexpected	Gr. 4 AE Expected	Gr. 4 AE Unexpected	Gr. 5 AE Expected or Unexpected
Unrelated Unlikely	Not required	Not required	5 calendar days [#]	5 calendar days	24 hours*
Possible Probable Definite	Not required	5 calendar days	5 calendar days [#]	5 calendar days	24 hours*
# If listed in protocol as expected and not requiring expedited reporting, event does not need to be reported.					
* For participants enrolled and actively participating in the study or for AEs occurring within 30 days of the last intervention, the AE should be reported within 1 business day of learning of the event.					

12.3.2 Serious Adverse Event (SAE)

A SAE is an adverse event that:

- Results in death. **NOTE:** Death due to disease progression should not be reported as a SAE, unless it is attributable by the site investigator to the study drug(s)
- Is life-threatening (defined as an event in which the subject was at risk of death at the time of the event; it does not refer to an event which hypothetically might have caused death if it were more severe)
- Requires inpatient hospitalization for >24 hours or prolongation of existing hospitalization. **NOTE:** Hospitalization for anticipated or protocol specified procedures such as administration of chemotherapy, central line insertion, metastasis interventional therapy, resection of primary tumor, or elective surgery, will not be considered serious adverse events.
- Results in persistent or significant disability/incapacity
- Is a congenital anomaly or birth defect
- Is an important medical event (defined as a medical event(s) that may not be immediately life-threatening or result in death or hospitalization but, based upon appropriate medical and scientific judgment, may jeopardize the subject or may require intervention (e.g., medical, surgical) to prevent one of the other serious outcomes listed in the definition above). Examples of such events include, but are not limited to, intensive treatment in an emergency room or at home for allergic bronchospasm; blood dyscrasias or convulsions not resulting in hospitalization; or the development of drug dependency or drug abuse.

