- Subjects who experience stable disease (SD) at the initial response assessment at 8 weeks from initiation of primary nivolumab therapy, with the subsequent scan in 8 weeks (± 7 days) documenting CR/PR which is maintained at the next imaging assessment in 8 weeks (± 7 days) (i.e., ~24 weeks from initiation of nivolumab).

Patients who have SD on initial assessment followed by CR/PR on first confirmatory assessment which does not persist on the second confirmatory imaging assessment will be allocated to Arm B as CR/PR was not persistent and confirmed on consecutive imaging assessments.

Subjects with confirmed PR/CR (arm A) will discontinue nivolumab and be followed with serial imaging assessments every 8 weeks. If progressive disease (PD) develops, therapy with nivolumab will be resumed and will not be discontinued if a subsequent PR or CR were to occur. Subjects who experience subsequent PD following re-initiation of nivolumab, will be treated with nivolumab + ipilimumab every 3 weeks x 2 doses and will continue nivolumab. All patients will continue on treatment with nivolumab alone every 4 weeks which will begin 5 weeks \pm 3 days after the last dose of nivolumab + ipilimumab. For subjects who experience a PD on nivolumab and ipilimumab, treatment will be discontinued.

If by 24 weeks, subjects have not demonstrated a persistent CR/PR confirmed on at least two serial scan assessments, then subjects will be allocated to Arm B at the 24 week time point.

Arm B (persistent PD/SD) includes the following patient scenarios:

- Subjects who experience PD at 8 weeks (initial response assessment) on primary nivolumab therapy which is then confirmed by a second scan within 4 weeks (\pm 7 days). The confirmatory scan is not required if the site investigator determines that this is clinically detrimental;
- Subjects who initially experience SD at 8 weeks (initial response assessment), which is confirmed with a second scan showing SD in 8 weeks (\pm 7 days)
- Subjects who have received at least 3 doses of nivolumab and may have signs and/or symptoms concerning for early clinical progression with radiographic evidence of PD before 8 weeks
- Subjects who do not meet the criteria for allocation into Arm A given lack of persistent CR/PR confirmation on serial and consecutive imaging within the first 6 months of the study will be allocated to Arm B by the 6-month time point.

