12.3 DF/HCC and BMS Expedited Adverse Event Reporting

Investigators must report to the Overall PI any serious adverse event (SAE) that occurs after the initial dose of study treatment, during treatment, or within 30 days of the last dose of treatment on the local institutional SAE form. All SAEs that occur following the subject's written consent to participate in the study through 30 days of discontinuation of dosing must be reported to BMS Worldwide Safety using the MedWatch Form 3500A, which can be accessed at <http://www.accessdata.fda.gov/scripts/medwatch/>. The BMS protocol ID number must be included on the MedWatch Form. SAEs, whether related or not related to study drug, and pregnancies must be reported to BMS within 24 hours. SAEs must be recorded on BMS or an approved form; pregnancies must be reported on a Pregnancy Surveillance Form.

SAE Email Address: [REDACTED]

SAE Facsimile Number: [REDACTED]

If only limited information is initially available, follow-up reports are required. (Note: Follow-up SAE reports should include the same investigator term(s) initially reported.)

If an ongoing SAE changes in its intensity or relationship to study drug or if new information becomes available, a follow-up SAE report should be sent within 24 hours to BMS (or designee) using the same procedure used for transmitting the initial SAE report.

All SAEs should be followed to resolution or stabilization.

The Sponsor will reconcile the clinical database SAE cases transmitted from BMS Global Pharmacovigilance (GPV&E) on a quarterly basis. BMS GPV&E will email, upon request from the Investigator, the GPV&E reconciliation report. Requests for reconciliation should be sent to [REDACTED]. The data elements listed on the GPV&E reconciliation report will be used for case identification purposes. If the Investigator determines a case was not transmitted to BMS GPV&E, the case should be sent immediately to BMS.

For multi-institution studies where a DF/HCC investigator is serving as the Overall Principal Investigator, each participating institution must abide by the reporting requirements set by the DF/HCC. This applies to any medical event equivalent to an unexpected grade 2 or 3 with a possible, probable or definite attribution, grade 4 toxicities, and grade 5 (death) regardless of study phase or attribution.

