12.6 Routine Adverse Event Reporting

All Adverse Events **must** be reported in routine study data submissions to the Overall PI on the toxicity case report forms. **AEs reported through expedited processes (e.g., reported to the IRB, FDA, etc.) must also be reported in routine study data submissions.**

Abnormal laboratory values or diagnostic test results constitute AEs only if they induce clinical signs or symptoms or require treatment or further diagnostic tests.

Wherever possible, timely confirmation of initial liver-related laboratory abnormalities should occur prior to the reporting of a potential drug-induced liver injury (DILI) event. All occurrences of potential DILIs, meeting the defined criteria, must be reported as SAEs.

Potential drug induced liver injury is defined as:

- 1) AT (ALT or AST) elevation > 3 times upper limit of normal (ULN)

AND

- 2) Total bilirubin > 2 times ULN, without initial findings of cholestasis (elevated serum alkaline phosphatase)

AND

- 3) No other immediately apparent possible causes of AT elevation and hyperbilirubinemia, including, but not limited to, viral hepatitis, pre-existing chronic or acute liver disease, or the administration of other drug(s) known to be hepatotoxic.

Hospitalization for elective surgery or routine clinical procedures that are not the result of an AE (e.g., surgical insertion of central line) should not be recorded as an AE.

Disease progression should not be recorded as an AE, unless it is attributable to the study regimen by the site investigator.

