13.5 Assessment of Safety

Adverse event reports are to be submitted within 28 days of each clinic visit. All relevant adverse events will be reviewed by the DSMC for up to 4 times each year or more frequently if requested by the DSMC.

Arm A: As part of the early safety monitoring to make sure that discontinuation of nivolumab is not detrimental for subjects with initial confirmed PR/CR, futility assessments will be implemented after 9 (~39%) of the 23 subjects have image assessment (8 +/- 7 days) since discontinuing nivolumab: an estimate of PD rate with a two-sided binomial CI will be constructed. If 5 or more of the first 9 subjects experience PD (i.e, to have a lower bound of the CI $\geq 25\%$), then the enrollment of arm A may be suspended. The following table gives the operating characteristics of the early futility stopping; if the true unknown probability of PD rate is 60% or higher, the probability of observing 5 or more subjects with PD will be greater than 48% at the time of the first subsequent image assessment after discontinuing nivolumab.

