13.7.2 Secondary Analysis

PFS and OS: The progression-free survival (PFS), and overall survival (OS) will each be summarized using the product-limit method of Kaplan-Meier. Median times for each endpoint will be presented with two-sided 90% confidence intervals estimated using log(-log(survival)) methodology. Kaplan-Meier estimates of PFS at 6 or 12 months may also be presented with two-sided 90% confidence intervals.

Salvage Therapy-Free Interval: The proportion of subjects re-start nivolumab since nivolumab discontinuation (arm A) during 1-year will be estimated with two-sided 90% confidence intervals. In addition, the reasons for re-starting nivolumab (Arm A) will be tabulated.

Subset analysis of study endpoints will be explored according to IMDC* risk group (favorable, intermediate, versus poor risk); prior systemic treatment for RCC (yes versus no); first line versus second line targeted therapy; histology (clear cell versus non-clear cell RCC subtypes; sarcomatoid components present versus absent)

*IMDC risk factors include ECOG < 1, time from original diagnosis to treatment less than one year, hemoglobin less than the lower limit of normal, and serum calcium, neutrophil count, or platelet count greater than the upper limit of normal

Immune Related Objective Response Rate: The proportion of subjects with immune ORR will be presented with two-sided 90% confidence interval estimated using exact binomial methods.

Safety and Tolerability: All adverse events recorded during the trial will be summarized for the safety population. The incidence of events that are new or worsening from the time of first dose of treatment will be summarized according to system organ class and/or preferred term, severity (based on CTCAE version 4), type of adverse event, and relation to study treatment.

The worst grade will be used if any toxicity event is reported multiple times on the same participant. All adverse events resulting in discontinuation, and/or dosing interruption, and/or treatment delay will also be summarized.

Given the potential multiple treatment sequences, the incidence of events (grade 3+) will be summarized according to treatment arms as well as the type of therapies they are on at the time of events.

Deaths reportable as SAEs and non-fatal serious adverse events will be listed by patient and tabulated by primary system organ class, and type of adverse event.

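### Deaths from progression after planned nivolumab discontinuation in Arm A can be missing from the safety death listing and from the early look, and the reporting sections do not give sites one rule for them

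*Combined protocol and SAP*

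**What the plan says.** Section 2.7 defines the Arm A strategy: "Subjects with confirmed PR/CR (arm A) will discontinue nivolumab and be followed with serial imaging assessments every 8 weeks". Section 13.5 gives the purpose of the early Arm A look as being "to make sure that discontinuation of nivolumab is not detrimental for subjects with initial confirmed PR/CR". The look is taken once 9 of the 23 subjects have been imaged after stopping, and enrollment to the arm may be suspended if 5 or more have progressed.

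Four passages bear on how a progression death is reported:

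- Section 12.3.2, within the SAE definition: "Death due to disease progression should not be reported as a SAE, unless it is attributable by the site investigator to the study drug(s".
- Section 12.6, on routine AE recording: "Disease progression should not be recorded as an AE, unless it is attributable to the study regimen by the site investigator".
- Section 12.3, last paragraph, on what participating institutions must report to DF/HCC. The duty reaches medical events generally and includes "grade 4 toxicities, and grade 5 (death) regardless of study phase or attribution".
- Section 12.3.1, whose table sets 24 hours for Grade 5 in both attribution rows. The footnote covers participants still active in the study, or within 30 days of the last intervention.

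SAE reports to the Overall PI cover events up to a limit: "within 30 days of the last dose of treatment on the local institutional SAE form". On the analysis side, Section 13.7.2 states: "Deaths reportable as SAEs and non-fatal serious adverse events will be listed by patient".

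**The concern.** In most oncology trials, excluding progression deaths from SAE reporting is sensible, because progression is the disease and the safety question is drug toxicity. Arm A is different. Its intervention is the absence of the drug, and the foreseeable harm is progression, and death from it, while off drug. A test that asks whether the drug caused the death is aimed at the wrong exposure.

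The exclusion would matter less if it governed only expedited forms, but Section 13.7.2 builds its death listing on SAE reportability. The display a reader would consult for deaths under the discontinuation strategy could therefore leave out the deaths most relevant to it. The early look does not make up for this if a death before the first scan is not an event. Sites working from different sections could also handle the same death differently in good faith.

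**Working it through.** This is mainly a reading of the text. The arithmetic in steps 5 and 6 only gives a sense of scale.

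**1. Which test applies?** Section 12.3.2 asks about the study drug(s). Section 12.6 asks about the study regimen, which could include planned discontinuation. The same death could fail the first test and meet the second.

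**2. Does the exclusion reach the analysis?** A progression death not attributed to drug is not an SAE (12.3.2). If it is also not attributed to the regimen, the progression is not recorded as an AE (12.6). It then appears neither in the AE summaries nor in the death listing of 13.7.2. Separately, SAE reporting to the Overall PI ends 30 days after the last dose. Arm A observation starts from that dose, so most of it lies outside the window, and later deaths of any cause may not be SAE-reportable either.

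**3. Do 12.3 and 12.3.1 agree with 12.3.2 and 12.6?** The first pair requires Grade 5 reports regardless of attribution and exempts no progression death. The second pair exempts them unless attributed. The 12.3 rule "SAEs, whether related or not related to study drug, and pregnancies must be reported to BMS within 24 hours" does not add to the conflict, because it applies only to events that already qualify as SAEs.

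**4. What does the early look count?** Its nine subjects are defined by having been imaged, and its event is PD. The text gives no way to count a death before the first off-drug scan. Suppose the first nine to stop include one such death, four with PD and four without. The plan waits for a ninth imaged subject. If that subject has not progressed, the count is 4 of 9 and the rule is not met. With the death counted it is 5 of 9 and the rule is met.

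**5. Scale, as an illustration only.** Inputs: 23 Arm A subjects (13.3) and median OS of 25.0 months on nivolumab in the phase III trial (2.2). Assumptions: exponential survival, at the full hazard or at half of it because Arm A subjects are responders.

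- Deaths in year 1, full hazard: 23 × (1 − 0.5^(12/25)) = 23 × 0.283 = 6.5.
- Deaths in year 1, half hazard: 23 × (1 − 0.5^(6/25)) = 23 × 0.153 = 3.5.
- Eight weeks is 8 × 12/52 = 1.846 months. Deaths among nine before an 8-week scan, full hazard: 9 × (1 − 0.5^(1.846/25)) = 9 × 0.0499 = 0.45.
- The same at half hazard: 9 × (1 − 0.5^(0.923/25)) = 9 × 0.0253 = 0.23.

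These are deaths of any cause. The year-1 figures include deaths after nivolumab is resumed or ipilimumab added, so they are not counts of deaths off drug. The share due to progression is not given.

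**6. Sensitivity of the look.** The exact chance of 5 or more events in 9 is 0.099 at a true rate of 30% and 0.267 at 40%. If counting pre-scan deaths raised the event rate by those ten points, a deliberately large step, the trigger probability would rise by 0.168. (The Section 13.6 table shows 0.03 and 0.1 at these rates. Those values match 6 or more of 9, which is a separate matter.)

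**The case against.** The strongest reply is that nothing is lost from the trial. OS counts death from any cause from nivolumab discontinuation, and PFS counts death as an event (13.2.2). Death is an off-study criterion whose date and reason go on the CRF (6.8). The DSMC may be given all deaths within 30 days of intervention (14.2). All of this stands, so a reader who infers that these deaths vanish from the safety record would be wrong. What is at risk is SAE reporting, one listing and one early rule.

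A reader might also infer that such deaths surface only through six-monthly survival contact. The documents do not support that. During observation, Arm A subjects are seen every 28 days or, on the extended schedule, every 8 weeks with calls at least every 4 weeks, and they are scanned every 8 weeks (Section 8, Arm A calendar). Six-monthly contact belongs to follow-up after treatment has ended.

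A third reply is that 12.3.2 defines SAEs for the Overall PI and BMS, while the end of 12.3 and the 12.3.1 table govern DF/HCC reporting, so a site could file a Grade 5 report without an SAE form. This partly stands, and it is too strong to say that the sections are flatly opposed or that no site could comply. Tension remains because the 12.3.1 table is headed as a table of AEs. A site that follows 12.6 and treats progression as no AE may conclude that it has nothing to report, while 12.3 reaches any medical event.

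Finally, 12.2 grades attribution to study treatment and includes a possible category, so an investigator might attribute a death to the strategy. The drug test is therefore a poor fit, not an impossible one.

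**Conclusion.** The concern holds in limited form. The attribution test in 12.3.2 does not suit an arm that tests stopping a drug, and it differs from the test in 12.6. Through 13.7.2, a progression death after planned discontinuation can be missing from the safety death listing. The 13.5 look has no place for a death before the first off-drug scan. The reporting sections need to be reconciled for these deaths.

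The size cannot be fixed from the documents. The illustrative 3.5 to 6.5 first-year deaths among 23 subjects rest on an exponential curve, on survival in patients not selected for response, and on an arbitrary half hazard. Fewer than one pre-scan death would be expected among the first nine. It is tempting to project deaths across all 83 subjects, but that would not measure this problem: it would include Arm B and long-term follow-up, much of it outside the reporting windows whatever 12.3.2 says.

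No primary, PFS or OS result changes. This is an inexpensive improvement to the safety display and the early rule, not a flaw that threatens the trial's conclusions.

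**What to change.** (a) In 13.7.2, list all deaths by arm, treatment phase at death (observation, resumed nivolumab, combination, off treatment) and cause. Dates of death are already collected for OS, and treatment phase follows from the dosing record. The planned summary of grade 3+ events by arm and therapy does not replace this, because it covers recorded adverse events.

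(b) In 13.5, define the nine as the first nine Arm A subjects to stop nivolumab. Count a death before the first off-drug scan as an event and keep that subject in the denominator. This is consistent with 13.4, whose analysis set already retains subjects who die before evaluation. Recompute the 13.6 probabilities for the rule as finally worded.

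(c) Reconcile 12.3, 12.3.1, 12.3.2 and 12.6 so that sites have one rule for progression deaths during Arm A observation. The edit should settle whether attribution is to drug or regimen and how the 30-day window applies to subjects in planned observation. The sponsor should choose the rule; what matters here is that there is only one.

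The cost is a wording amendment, one extra listing, possibly a few more death reports, and a slightly more sensitive early rule. No dose or schedule changes.

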12.3.3 Unexpected Adverse Event

For this study, an AE is considered unexpected when it varies in nature, intensity or frequency from information provided in the current IB, prescribing information or when it is not included in the informed consent document as a potential risk. Unexpected also refers to AEs that are mentioned in the IB as occurring with a class of drugs or are anticipated from the pharmacological properties of the drug, but are not specifically mentioned as occurring with the particular drug under investigation.

12.4 Expedited Reporting to the Food and Drug Administration (FDA)

The Overall PI, as study sponsor, will be responsible for all communications with the FDA. The Overall PI will report to the FDA, regardless of the site of occurrence, any serious adverse event that meets the FDA's criteria for expedited reporting following the reporting requirements and timelines set by the FDA.

12.5 Expedited Reporting to Hospital Risk Management

Participating investigators will report to their local Risk Management office any participant safety reports or sentinel events that require reporting according to institutional policy.

12.6 Routine Adverse Event Reporting

All Adverse Events **must** be reported in routine study data submissions to the Overall PI on the toxicity case report forms. **AEs reported through expedited processes (e.g., reported to the IRB, FDA, etc.) must also be reported in routine study data submissions.**

Abnormal laboratory values or diagnostic test results constitute AEs only if they induce clinical signs or symptoms or require treatment or further diagnostic tests.

Wherever possible, timely confirmation of initial liver-related laboratory abnormalities should occur prior to the reporting of a potential drug-induced liver injury (DILI) event. All occurrences of potential DILIs, meeting the defined criteria, must be reported as SAEs.

Potential drug induced liver injury is defined as:

- 1) AT (ALT or AST) elevation > 3 times upper limit of normal (ULN)

AND

- 2) Total bilirubin > 2 times ULN, without initial findings of cholestasis (elevated serum alkaline phosphatase)

AND

- 3) No other immediately apparent possible causes of AT elevation and hyperbilirubinemia, including, but not limited to, viral hepatitis, pre-existing chronic or acute liver disease, or the administration of other drug(s) known to be hepatotoxic.

Hospitalization for elective surgery or routine clinical procedures that are not the result of an AE (e.g., surgical insertion of central line) should not be recorded as an AE.

Disease progression should not be recorded as an AE, unless it is attributable to the study regimen by the site investigator.

